6. **PEG:** The PEG is a reliable and valid 3-item scale of pain intensity and interference. Patients rate the pain's intensity and interferences with their enjoyment of life and general activity on a numeric rating scale ranging from 0 ("no pain" or "does not interfere") to 10 ("pain as bad as you can imagine" or "completely interferes").

7. **PROMIS Fatigue:** The Patient Reported Outcomes Measurement Information System (PROMIS) Fatigue Scale is a 4-item scale that measures fatigue impact and fatigue experience. Patients rate how much fatigue they have experienced and how much fatigue has bothered them on a 5-point Likert-type scale ranging from 0 ("not at all") to 5 ("very much").

8. **ISI:** The Insomnia Severity Index is a 7 item reliable and valid instrument to quantify perceived insomnia severity.

9. **Constipation and Numbness/Tingling:** These symptoms will each be assessed by one question asking how much the symptom distressed or bothered the respondent in the last week using a 6 point Likert-type scale from no symptom to very bothersome.

10. **KCCQ-12:** The Kansas City Cardiomyopathy Questionnaire is a 12-item self-administered validated questionnaire (administration time 5-10 minutes) that measures CHF-specific health status. It is a shortened version of the KCCQ 23 item measure which is reliable, sensitive to clinical change, and predicts hospitalization and mortality. Additionally, we will ask two questions assessing how bothersome symptoms are. It will be administered to Veterans with CHF.

11. **CCQ:** The Clinical COPD Questionnaire is a self-administered 10-item measure of COPD symptoms, functioning, and emotional well-being. It is well-validated, reliable, and responsive. It will be administered to Veterans with COPD.

12. K-BILD: The King's Brief Interstitial Lung Disease is a 15-item self-completed health status measure for ILD. It is validated and can be used to assess ILD from the patient's perspective. It will be administered to Veterans with ILD.

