(CAN) score will be used to define a population at increased risk for hospitalizations or death that is likely to need the palliative care intervention because of increased illness severity. The CAN is a VA-developed prognostic tool that was created to help primary care proactively identify and manage at risk Veterans on a population level. We will collect the CAN score on all potential subjects with a diagnosis of CHF, COPD, or ILD as defined in Table 1. A CAN score of  $\geq 80$  for those with CHF or COPD was chosen in consultation with the VA Central Offices of Primary Care and Palliative Care. Preliminary studies identified 5,951 Veterans total at both sites with CHF or COPD and a CAN score of  $\geq 80$ . The CAN score may not be as valid for the small number of patients with ILD, thus we will not use it as an eligibility criterion.

To enroll a sample with poor quality of life who is appropriate for the intervention, potential participants will need to report a Functional Assessment of Chronic Illness Therapy-General (FACT-G) score  $\leq 70$  and be bothered by one of the intervention target symptoms. The FACT-G is a widely-used, valid, reliable quality of life measure that is the primary outcome in this study. It measures physical, social/family, emotional, and functional well-being. A score of  $\leq 70$  identifies poor quality of life as validated by declining performance status and increasing disease burden.

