#### Randomization - Aim 1:

Randomization will occur at the patient level with 1:1 randomization of patients to intervention or control groups. Randomization will be computer generated using random block sizes and stratified by site and disease CHF, ILD, or COPD, or both CHF and COPD.

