The primary outcome will be the difference in FACT-G score at 6 months. Because of the anticipated high correlation of baseline FACT-G with follow-up FACT-G ( $r>0.5$ ), we will include the baseline FACT-G as a precision variable in the mixed model. To describe the treatment by disease interaction, we will estimate the treatment effect and its confidence interval within each of the disease groups (CHF, ILD, COPD) using disease-specific health status measures (KCCQ, K-BILD, CCQ) at the 6 month endpoint. In exploratory analyses, we will estimate treatment effect within illness subgroups (CHF, ILD, and COPD) on the primary outcome, and within subgroups of illness, including CHF (preserved vs. reduced ejection fraction) and COPD (defined by spirometry and imaging). Missing data will be reviewed to identify potential patterns and examined to assess how these patterns impact our results. Specifically, we will examine plots of group means over time stratified by the time of the last completed observation to determine if biases are evident due to missing data. When data are missing at random, unbiased results can still be obtained from the likelihood method used in the analysis. To account for the possibility of data missing not at random, sensitivity analyses will be performed using pattern mixture models and results will be presented to assess the impact of missing data on the reported conclusions. Among those who were hospitalized or died, we will examine for differences in

intensive care utilization and patterns of care at the end of life. We will also examine for intervention effect on longer term health care utilization (e.g., hospitalization, intensive care utilization).

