**Advancing Symptom Alleviation With Palliative Treatment (ADAPT)**  
**NCT02713347**  
**IIR 14-346**

**November 15, 2021**

**ADAPT Data Analysis Plan:**

Data from all participants will be included regardless of level of participation using an intent-to-treat approach. The primary outcome measure, FACT-G, will be analyzed as a continuous variable, while the secondary outcomes will be either continuous (disease-specific health status, depression, symptom burden, emergency department visits, hospitalizations) or binary (advance care planning communication and documentation; mortality).. Analysis models will adjust for the disease stratification variable used in randomization. Analyses of the repeated measures, including primary and secondary endpoints, will be performed with SAS 9.4 using maximum likelihood estimation (MLE) for incomplete data using linear mixed models for continuous outcomes and generalized linear mixed models with a logit link for binary endpoints. This approach has several advantages: 1) all available data on eligible subjects can be included in the analysis even when there are missing data at follow-up, 2) MLE estimates the correlation between related measures and adjusts test statistics appropriately, 3) time-varying covariates can be incorporated into the model, if desired, and 4) the assumptions about missing data are relaxed from missing completely at random to missing at random (Little RJ. Methods for handling missing values in clinical trials. *J Rheumatol* 1999;26(8):1654-1656). The primary analyses will not consider the pre-randomization variables, but the effect of these variables on outcomes will be investigated as secondary analyses.

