The primary outcome will be the difference between intervention and control in the change in FACT-G from baseline to 6 months. To describe the treatment by disease interaction, we will estimate the treatment effect and its confidence interval within each of the disease groups. Missing data will be reviewed to identify potential patterns and examined to assess how these patterns impact our results. Specifically, we will examine plots of group means over time stratified by the time of the last completed observation to determine if biases are evident due to missing data (Fairclough DL. Design and analysis of quality of life studies in clinical trials. CRC press; 2nd Edn, 2010). When data are missing at random, unbiased results can still be obtained from the likelihood method used in the analysis. If we find evidence of data missing not at random, sensitivity analyses will be performed using pattern mixture models (Little RJ, Wang Y. Pattern-mixture models for multivariate incomplete data with covariates. *Biometrics* 1996;52(1):98-111) and results will be presented to assess the impact of missing data on the reported conclusions.

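### Maximum likelihood without a small-sample degrees-of-freedom method will make the K-BILD interval in the small ILD group somewhat too narrow; REML with Kenward-Roger corrects this, and the primary FACT-G result is unaffected

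*SAP*

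**What the plan says.** The SAP (ADAPT Data Analysis Plan) states that repeated measures, primary and secondary, will be analysed in SAS 9.4 "using maximum likelihood estimation (MLE) for incomplete data using linear mixed models for continuous outcomes". The protocol's Aim 1 Data Analysis says the same. Neither document mentions REML or a method for denominator degrees of freedom. Disease-specific health status is one of the continuous secondary outcomes covered by that sentence.

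On disease groups the SAP says "we will estimate the treatment effect and its confidence interval within each of the disease groups", as a description of the treatment-by-disease interaction, and "Analysis models will adjust for the disease stratification variable used in randomization". The protocol (Aim 1 Data Analysis) is more specific: the within-disease estimates are to be made "using disease-specific health status measures (KCCQ, K-BILD, CCQ) at the 6 month endpoint". FACT-G by illness is exploratory there.

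Of K-BILD, the protocol (section IV.A) says "It will be administered to Veterans with ILD". Table 5 schedules it at baseline and at months 4 and 6. No ILD number is given. The only indication of size is in the text after the eligibility table: "The CAN score may not be as valid for the small number of patients with ILD".

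**The concern.** ML estimates the covariance as if the mean parameters were known. In a large sample that costs nothing; in a small one it gives standard errors that are too small and intervals that are too short. A normal reference distribution, which the SAP does not rule out, shortens them further.

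The plan commits to an interval in each disease group, and one group is small. If that interval is too narrow, a chance ILD result looks firmer than it is. The pilot work listed in the protocol's Preliminary Studies is in CHF and COPD, with none in ILD, so there is little earlier evidence against which to judge a surprising ILD finding.

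**Working it through.** **The plan's own figure.** Table 3 gives 114 per arm for an effect size of 0.40, 85% power and two-sided alpha 0.05. The noncentral t calculation gives 114, and 85.6% power at the 115 completers per arm in the Sample Size section. The documents give no figure for ILD precision to reproduce.

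**Formula.** For a comparison at one time point with complete data, n patients and p mean parameters, the ML variance is (n − p)/n times the REML variance. So

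- SE ratio, ML to REML = √((n − p)/n)
- coverage with a t reference = P(|T| < t₀.₉₇₅ × ratio), T on n − p df
- coverage with a normal reference = P(|T| < 1.96 × ratio)

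REML with Kenward-Roger gives exactly 95% in this case.

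**(a) Primary comparison.** n = 2 × 115 = 230, p = 2. Ratio √(228/230) = 0.996. Coverage is 94.9% (t) or 94.8% (normal).

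**(b) Pooled treatment-by-disease model.** Randomisation is "stratified by site and disease CHF, ILD, or COPD, or both CHF and COPD", so there are four disease strata by two arms, p = 8. The protocol's stated losses of 20% to 25% of 400 leave 300 to 320 patients. Ratio √(292/300) = 0.987 to √(312/320) = 0.987: the ILD standard error is about 1.3% too small, with coverage 94.6% to 94.7%. With 230 patients the ratio is √(222/230) = 0.982, and coverage is 94.5% (normal) to 94.6% (t).

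**(c) K-BILD, ILD patients only.** p = 2; n is assumed.

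| ILD n (total) | SE ratio | Coverage, ML with t | Coverage, ML with normal |
|---|---|---|---|
| 10 | √(8/10) = 0.894 | 92.7% | 88.2% |
| 20 | √(18/20) = 0.949 | 93.8% | 92.1% |
| 30 | √(28/30) = 0.966 | 94.2% | 93.1% |
| 40 | √(38/40) = 0.975 | 94.4% | 93.6% |

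For example, at n = 20, t₀.₉₇₅ on 18 df is 2.101, and 2.101 × 0.949 = 1.99; P(|T₁₈| < 1.99) = 93.8%. A baseline covariate makes p = 3 and lowers these a little: at n = 20, ratio 0.922 and coverage 93.2% with t.

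The reference distribution matters about as much as the estimator. At n = 20, REML with a normal reference would cover P(|T₁₈| < 1.96) = 93.4%, against 93.8% for ML with t.

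**(d) With dropout.** Simulation of three visits with an unstructured covariance, dropout of about 22% missing at random, and assumed correlations of 0.55 to 0.65 (1,500 runs, Monte Carlo SE roughly 0.6 to 0.9 points):

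| ILD n | ML, normal | ML, t on n − 2 | REML + Kenward-Roger | Median width, KR to ML with t |
|---|---|---|---|---|
| 12 | 87.5% | 91.5% | 94.5% | 1.17 |
| 20 | 90.0% | 92.8% | 94.3% | 1.10 |

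**The case against.** A reader might infer that every planned ILD interval is too narrow, FACT-G included. The documents do not support that. The SAP puts the disease stratum in its models and presents the within-disease estimates as describing an interaction, straight after defining the FACT-G outcome. That wording favours one pooled model, in which the narrowing is trivial (b). The SAP sentence does not name K-BILD; that link comes from the protocol. This part of the objection stands, and it limits the point to K-BILD. It does not remove it: disease-specific health status is an outcome of the SAP's own linear mixed models, and no other patients have K-BILD data to pool with.

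A reader might also infer that the error favours the intervention. It does not. The interval is too short on both sides and the estimate is not shifted, so a chance harm would look as certain as a chance benefit.

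The size is open to challenge. It rests on an ILD number, correlations and a reference distribution that the documents do not give, and the worst figures need the normal reference as well as ML. With 40 patients and a t reference the loss is about half a percentage point (94.4%).

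Finally, no ILD test, alpha or claim is specified, and even a correct ILD interval will be wide. With the protocol's FACT-G SD of 15 and unadjusted scores, the half-width at n = 20 is 2.101 × 15 × √(4/20) = 14 points, against a minimal important difference of 4 to 6. That is fair, and it is why this is a minor point. It is also possible that MLE was meant loosely, for any likelihood method; if so, the same edit removes the ambiguity.

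**Conclusion.** The point holds for K-BILD in ILD and is minor. Followed as written, the SAP gives a K-BILD standard error about 2.5% (n = 40) to 11% (n = 10) too small. The interval covers about 92.7% to 94.4% with complete data and a t reference, and less with dropout or a normal reference. This assumes 10 to 40 ILD patients in total and two mean parameters. The direction does not depend on those assumptions; the size does.

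The primary FACT-G analysis is essentially unaffected (ratio 0.996), and so is a pooled within-disease FACT-G analysis (about 1.3%). If the within-disease FACT-G effects were instead fitted separately by disease, the ILD figures in (c) would apply to them too. The SAP does not say which is intended.

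**What to change.** In the SAP, replace maximum likelihood by REML for the linear mixed models, with Kenward-Roger standard errors and degrees of freedom (METHOD=REML, DDFM=KR in SAS 9.4). This matters above all for K-BILD in ILD. Add one sentence saying whether within-disease FACT-G effects come from a pooled interaction model or from separate models. REML uses all available data under the same missing-at-random assumption, so the advantages the SAP lists for its approach are kept.

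The change has costs:

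- The ILD-only interval widens by a median of about 10% at n = 20 and 17% at n = 12, against ML with t. That is the correction working, but it should be expected. A pooled ILD interval would widen by about 1.7%.
- REML likelihoods cannot be used to compare models with different fixed effects. Any such comparison needs an ML fit.

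The change does not address the logit models in the same small group. Nor does it protect a pooled model against a different ILD variance. If 20 of 400 patients had ILD with an SD 25% larger, the pooled variance would be (380 + 20 × 1.5625)/400 = 1.028 times the common value. Coverage would then be about 88% under ML and 89% under Kenward-Roger. Design, data collection and the primary conclusion stay as they are.

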*Primary/Secondary Analyses.* Data from all participants will be included regardless of level of participation using an intent-to-treat approach. The primary outcome measure, FACT-G, will be analyzed as a continuous variable, while the secondary outcomes will be either continuous (disease-specific health status, depression, symptom burden, emergency department visits, hospitalizations) or binary (advance care planning communication and documentation; mortality). Due to the short follow-up period, time-to-event analyses will not be used. Analyses of the repeated measures, including primary and secondary endpoints, will be performed with SAS 9.4 using maximum likelihood estimation (MLE) for incomplete data using linear mixed models for continuous outcomes and generalized linear mixed models with a logit link for binary endpoints. This approach has several advantages: 1) all available data on eligible subjects can be included in the analysis even when there are missing data at follow-up, 2) MLE estimates the correlation between related measures and adjusts test statistics appropriately, 3) time-varying covariates can be incorporated into the model, if desired, and 4) the assumptions about missing data are relaxed from missing completely at random to missing at random. The primary analyses will not consider the pre-randomization variables, but the effect of these variables on outcomes will be investigated as secondary analyses. We will add a random intercept for PCP to the analytic models to account for clustering of outcomes by practice patterns.

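### The SAP's primary contrast is a difference in FACT-G change with no stated role for baseline FACT-G, and neither document puts site in the model; stating both is a minor fix

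*SAP*

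**What the plan says.** **Protocol, section F, Aim 1 Data Analysis.** The endpoint is the month-6 score: "The primary outcome will be the difference in FACT-G score at 6 months". Baseline is then given a role. "Because of the anticipated high correlation of baseline FACT-G with follow-up FACT-G" (r above 0.5), the protocol says, "we will include the baseline FACT-G as a precision variable in the mixed model". A clustering term is also promised: "We will add a random intercept for PCP to the analytic models".

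**SAP, ADAPT Data Analysis Plan.** The endpoint becomes a change: "The primary outcome will be the difference between intervention and control in the change in FACT-G from baseline to 6 months". The baseline precision term and the provider (PCP) random intercept do not appear, and neither omission is explained. One stratification factor is named: "Analysis models will adjust for the disease stratification variable used in randomization". On incomplete data, the SAP says that "all available data on eligible subjects can be included in the analysis even when there are missing data at follow-up".

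**Both documents** carry the statement that "The primary analyses will not consider the pre-randomization variables". Neither makes an exception, although the protocol adjusts for baseline FACT-G and the SAP adjusts for disease.

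**Protocol, Randomization – Aim 1.** Randomization is stratified by site as well as by disease group. Neither analysis section names site as a model term.

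**The concern.** The trial has one primary endpoint, and the SAP does not fix the model for it. Three forms fit its words: baseline as a covariate, baseline as a response with one mean shared by the arms, or baseline as a response with its own mean in each arm. The first two use the fact that randomization makes the arms equal at baseline in expectation. The third does not, and its arm-by-visit change contrast carries chance baseline differences into the result.

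At stake is the width of the confidence interval and some power in the lower part of the 4–6 point range that the protocol (Sample Size) gives as clinically important. Baseline FACT-G is already collected on everyone, so nothing is saved by leaving it unused. The site omission is a separate matter: a factor that restricted the randomization should be in the model that produces the standard error.

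**Working it through.** **Inputs from the documents**
- Two-sided alpha 0.05, effect size 0.4, SD 15 (so 6 points), about 115 completers per arm (Protocol, Sample Size).
- 400 randomized 1:1, so N = 200 baselines per arm. With 5% deaths and 20% missing outcomes, 200 × 0.75 = 150 per arm have a month-6 value. The section states 115, so both figures are carried.
- r above 0.5 between baseline and follow-up (Protocol, Aim 1 Data Analysis). I show 0.5 to 0.7.
- FACT-G of 70 or less at entry (Protocol, Table 1).

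**Assumptions.** SD 15 is the SD of the score at both times (the protocol does not say whether it is of the score or of change). Non-completers contribute a baseline only.

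**1. The plan's own figure.** SE = 15 × √(2/115) = 1.978; 6/1.978 − 1.96 = 1.07; power 85.8% (85.6% with the t distribution). The stated 85% reproduces.

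**2. Formulas.** Let n be completers per arm, s0 and s1 the baseline and month-6 SDs, and b = r × s1/s0.
- Baseline-adjusted, or common baseline mean: V = 2 × s1² × (1 − r²)/n.
- Separate baseline means: V + 2 × (1 − b)² × s0²/N.
- With s0 = s1 the variance ratio is 1 + (n/N) × (1 − r)/(1 + r).

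**3. SD 15 at both times**

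| n | r | Variance ratio | SE, separate vs adjusted | Power, 5 points |
|---|---|---|---|---|
| 115 | 0.5 | 1 + 0.575/3 = 1.19 | 1.870 vs 1.713 | 76.2% vs 83.1% |
| 115 | 0.6 | 1.14 | 1.692 vs 1.583 | 84.0% vs 88.5% |
| 115 | 0.7 | 1.10 | 1.483 vs 1.413 | 92.1% vs 94.3% |
| 150 | 0.5 | 1 + 0.75/3 = 1.25 | 1.677 vs 1.500 | 84.6% vs 91.5% |
| 150 | 0.6 | 1.19 | 1.510 vs 1.386 | 91.2% vs 95.0% |
| 150 | 0.7 | 1.13 | 1.316 vs 1.237 | 96.7% vs 98.1% |

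At r = 0.5, power for 4 points is 57% vs 65% (n = 115) or 67% vs 76% (n = 150). For the planned 6 points it is 89% vs 94%, or 95% vs 98%.

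A generalized least squares calculation with all four visits and equal correlations gives the same SEs. If every non-completer also supplies month 4, the ratio at r = 0.5 is 1.20 (n = 115) or 1.26 (n = 150).

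**4. Narrower baseline spread.** The entry limit may shrink s0; the documents do not say by how much. I assume 10 to 12.
- Holding r and s1 = 15 fixed, the slope b rises towards 1 and the ratio is 1.00–1.09. The 5-point loss at r = 0.5 and s0 = 12 is about 2.5 percentage points (80.6% vs 83.1%, n = 115).
- Holding the slope at 0.5 and the residual variance at 225 × 0.75, s0 = 12 gives a ratio of 1.12 (n = 115) or 1.16 (n = 150). Power for 5 points is 78.7% vs 83.1%, or 87.2% vs 91.5%, a loss of about 4.4 percentage points.

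The loss under a narrowed baseline therefore runs from near zero to between 4 and 5 points, depending on the slope.

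**5. Site and provider.** The documents give no between-site or between-provider variance, so the effect of including or omitting either term cannot be calculated.

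**The case against.** The strongest defence is that the loss depends on one unstated reading. The protocol commits to baseline FACT-G in the model, and the SAP nowhere withdraws that or says that it supersedes the protocol. The sentence on pre-randomization variables is weak evidence of exclusion: in the protocol it already stands beside the baseline term, and in the SAP beside disease adjustment, so its authors cannot have meant it literally. That stands. What remains is that the SAP reworded the endpoint, dropped the covariate sentence and named no baseline constraint. A mixed model handles baseline efficiently only if told to.

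It is also fair that r = 0.5 is the lower edge of what the protocol expects and that SD 15 at baseline may be too wide for a population selected on FACT-G. Both shrink the loss, as shown.

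A reader might infer more than the documents support:
- *That the trial is biased or underpowered.* Under randomization every form targets the same treatment effect, and the least precise form still gives about 89% power for 6 points at r = 0.5. If 15 is instead the SD of change, complete pairs alone give the 85.8% of step 1.
- *That the variance penalty is a third at r = 0.5 (2(1 − r) against 1 − r²).* That holds for complete pairs only. The SAP keeps all available data, so the extra baselines reduce it to 19–25%.
- *That naming site buys precision.* No figure in the documents supports a size for that.

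**Conclusion.** The point holds as a minor one. The SAP does not say how baseline FACT-G enters its primary model, does not carry over the protocol's term for it, and omits site although site was a stratification factor. If baseline is fitted with separate arm means, the variance of the primary contrast is 10–19% larger with 115 completers per arm, or 13–25% larger with 150, for r from 0.7 to 0.5 and SD 15 at both times. Power for 5 points is then about 2 to 7 percentage points lower with 115 completers. With a common baseline mean or a baseline covariate nothing is lost. The cost is forgone precision, with no bias and no shortfall against the stated 85% power. The case for site rests on agreement with the randomization alone.

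**What to change.** In the SAP, write: *Primary analysis: linear mixed model with FACT-G at baseline and at 4, 6 and 12 months as responses; terms for visit, arm-by-visit with a common baseline mean across arms, disease stratum and site. The primary contrast is the arm difference at month 6, which in this model equals the difference in change from baseline to month 6.* This form keeps patients who have only a baseline value, in line with the SAP's aim of including all participants.

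Then:
- in both documents, limit the sentence on pre-randomization variables to variables other than baseline FACT-G, disease stratum and site;
- use the same wording for the primary contrast in the protocol and the SAP;
- state whether the PCP random intercept is kept.

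If this is done before outcome data are seen, the cost is wording only: no new data, visits or patients. The SAP is dated November 15, 2021, and the documents do not say whether outcomes had been seen by then. If they had, report the model actually used and show the baseline-adjusted result beside it, labelled as added; the cost is one extra analysis.

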#### Sample Size

The sample size was planned to detect a clinically significant change on the primary outcome, quality of life. We plan to enroll 400 Veterans and anticipate 5% will die and 15-20% will have missing outcome data because they did not complete surveys or dropped out. Thus approximately 115 Veterans per arm will complete the study. With this sample size, we will have 85% power to detect a moderate effect size of 0.4 (two-sided test, alpha=0.05). The minimal clinically important difference on the FACT-G is 4-6 points, and with a standard deviation of 15, a Cohen's d effect size of 0.4 will be on the high end of clinical significance. We believe this is appropriate as this is a personnel-intensive intervention. **Table 3** illustrates a range of sample sizes per study arm with different power and effect size assumptions.

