**D. Description, Risks and Justification of Procedures and Data Collection Tools:**

**Aim 1:** Study personnel will administer measures four times: enrollment (baseline), 4 months, 6 months and 12 months (**Table 5**). The baseline and 6-month measures which are comprised of approximately 120 questions and are expected to last 45 minutes, will be obtained during an in-person visit, by mail and phone or by video teleconference. We will allow patients to complete 4 month and 12 month measures by mail or phone if they prefer. Veterans will be offered an incentive for completing each of the 4 study visits (\$10 at baseline, \$10 at 4 months, \$15 at 6 months, \$10 at 12 months). Patient reported survey data is necessary to achieve study aims as the primary outcome is quality of life which is patient perceived. Demographic data and information from medical record review is necessary to determine secondary outcomes. We have implemented the following protections:

Table 5. Study Visits and Assessments	Baseline	Month 4	Month 6	Month 12
Demographics/study form	X			
FACT-G (primary outcome)	X	X	X	X
PHQ-8, GAD-7	X	X	X	
KCCQ-12, CCQ, K-BILD	X	X	X	
QUAL-E, Symptom Assessment, GSDS	X		X	
Advance care planning communication, assess for advance directive documentation	X		X	
Medications	X		X	
Health care utilization, vital status, risk of hospitalization/death			X	X
Use of other medical services	X		X	

Satisfaction	X	X
--------------	---	---

Medical record data will be gathered for up to ten years after each participant concludes active study participation. The purpose of this is to determine the effect of the intervention on long-term health and health care use. This could include but is not limited to hospital discharge summaries, progress notes, operative notes, laboratory results, and diagnostic tests.

Protection against loss of confidentiality.

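### The SAP runs the missing-not-at-random sensitivity analysis only if evidence for it is found, but observed data cannot settle that condition and no criterion is given

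*SAP*

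**What the plan says.** The protocol (section F, Aim 1 Data Analysis) commits to the analysis outright: "To account for the possibility of data missing not at random, sensitivity analyses will be performed using pattern mixture models". The SAP, dated November 15, 2021, keeps nearly all of the surrounding text but changes this clause to "If we find evidence of data missing not at random, sensitivity analyses will be performed using pattern mixture models".

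For looking at the missing data, the SAP says "Missing data will be reviewed to identify potential patterns and examined to assess how these patterns impact our results". More specifically, "we will examine plots of group means over time stratified by the time of the last completed observation", the aim being "to determine if biases are evident due to missing data". The protocol plans the same plots, but there they do not decide whether the sensitivity analysis is done.

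The primary analysis is a likelihood-based mixed model. Among its advantages the SAP lists that "the assumptions about missing data are relaxed from missing completely at random to missing at random", so the primary result rests on MAR. FACT-G is collected at every visit (protocol section D and Table 5): "Study personnel will administer measures four times: enrollment (baseline), 4 months, 6 months and 12 months". On the expected loss, the protocol's Sample Size section says the investigators "anticipate 5% will die and 15-20% will have missing outcome data".

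**The concern.** A sensitivity analysis for MNAR is needed because the observed data cannot show whether MAR holds. Making it depend on finding evidence of MNAR reverses that logic. An unremarkable set of plots would be taken as a reason to skip the analysis, although such plots are compatible with a material departure from MAR.

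The SAP also names no threshold, test or decision-maker. Whether the check is run would be decided by someone looking at results by arm, which is what prespecification is meant to prevent.

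The stakes are real in this trial. The primary outcome is patient-reported, and the CHF and COPD patients are selected for high risk of hospitalization and death. Only the intervention arm has regular nurse and social-worker contact, and an attention control was ruled out (protocol, Control Group). Reasons for non-completion could therefore differ by arm, although the documents do not show that they will.

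**Working it through.** **1. The two texts.**

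| | Protocol, Aim 1 Data Analysis | SAP |
|---|---|---|
| Review of patterns, stratified plots | Yes | Yes |
| Pattern-mixture analysis | Always, because MNAR is possible | Only if evidence of MNAR is found |
| Rule for what counts as evidence | Not needed | None stated |
| Reason for the change | – | None stated |

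**2. What the diagnostics can show.** Write the joint distribution as f(observed scores, missingness pattern) × f(unobserved scores | observed scores, pattern). Every table and plot of observed data depends on the first factor only. MAR is an assumption about the second. Two worlds that share the first factor and differ in the second give identical plots, and only one of them is MAR.

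**3. A numerical example of both failures** (all parameters assumed). In a large simulated group, dropout after month 4 depended only on the observed month-4 score, so the data were MAR; 18.7% were missing at month 6.
- *The plots can look alarming under MAR.* The month-4 mean was 53.6 in dropouts and 60.2 in completers.
- *The plots can miss MNAR.* Lowering only the unseen month-6 scores by 6 points changes no plotted value. The true month-6 mean falls from 58.3 to 57.2, while the MAR-based estimate stays at 58.3.

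**4. The plan's own design figure.** Inputs from the Sample Size section: 115 completers per arm, effect size 0.4, SD 15, two-sided alpha 0.05. Power = Φ(0.4 × √(115/2) − 1.96) = Φ(3.03 − 1.96) = 0.858, against the stated 85%. It reproduces. The target difference is 0.4 × 15 = 6 points.

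The figure of 115 does not follow from the stated losses. With 200 randomized per arm and 20–25% lost in total, 150–160 remain; 115 would imply 1 − 115/200 = 42.5% loss. The percentages are used below.

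**5. Size of an undetected departure.** Let m be the fraction missing at 6 months and δ the amount by which unseen scores fall below the MAR prediction. The estimate moves by m(intervention) × δ(intervention) − m(control) × δ(control). The values of δ are assumptions; 6 points is the design effect, used as a round reference.

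| Scenario | Shift in estimate (points) |
|---|---|
| 15% missing, δ = 3, one arm | 0.15 × 3 = 0.45 |
| 20% missing, δ = 3, one arm | 0.20 × 3 = 0.6 |
| 15% missing, δ = 6, one arm | 0.15 × 6 = 0.9 |
| 20% missing, δ = 6, one arm | 0.20 × 6 = 1.2 |
| 20–25% missing (deaths counted), δ = 6, one arm | 1.2 to 1.5 |
| δ = 6 in both arms, 20% vs 15% missing | 1.2 − 0.9 = 0.3 |

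**6. Relative to the standard error.** SE = 15 × √(2/n): 1.68 at n = 160 and 1.73 at n = 150. Baseline adjustment with an assumed correlation of 0.5 multiplies these by √0.75, giving 1.45 and 1.50. Pairing 15% missing with 160 per arm and 20% with 150, the ratio runs from 0.9/1.68 = 0.54 to 1.2/1.50 = 0.80.

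**7. When it would and would not change the conclusion.**
- A full 6-point effect survives: 6 − 1.2 = 4.8, and 4.8/1.73 = 2.8. Removing it entirely would need a one-arm departure of 6/0.25 = 24 to 6/0.15 = 40 points.
- A smaller effect might not survive. An estimate of 3.5 with SE 1.5 has z = 2.33 and p ≈ 0.02. Less 1.2 points, z = 1.53 and p ≈ 0.13.
- An estimate of 5 would become 3.8, below the protocol's 4–6 point minimal important difference.

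**The case against.** The strongest reply is that evidence is not proof. Differences between dropouts and completers, recorded hospitalizations, deaths and follow-up rates all make MNAR more or less plausible, and the SAP does not confine evidence to the plots. That is true. None of these sources can exclude MNAR, however, so the condition remains an unsafe reason to omit the analysis.

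Neither document says the SAP overrides the protocol, so it could be argued that the protocol's commitment still stands. That leaves two inconsistent instructions and does not make the condition sound.

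The SAP also keeps its pattern review and plots whatever happens, so missing data would not go unexamined. These give no treatment estimate under MNAR.

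The likely impact at the design effect is modest, and the departures are assumed. This stands and is reflected in the figures. The example in step 3 also works by construction: it illustrates a known identity and measures nothing about this trial.

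The best criticism concerns the remedy. The protocol's sentence gives no patterns, identifying restrictions or shifts, and under monotone dropout some identifying restrictions are equivalent to MAR. Restoring the sentence alone would move the discretion from whether to run the model to how. This stands, and the fix takes it up.

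**Conclusion.** The concern holds. The protocol's commitment is unconditional and the SAP's is conditional. The condition has no criterion, and the scores observed at the four visits cannot separate MAR from MNAR. The only planned analysis that relaxes MAR can thus be dropped after the data are seen.

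The consequence is moderate. The primary model, sample size and power are unaffected, and a 6-point effect would withstand the departures considered. The check matters for an estimate near the significance boundary or near the lower end of the minimal important difference. This sizing assumes the protocol's 15–20% missing data, SD 15 and a departure of 3–6 points confined to one arm. The finding that the condition is unsound needs none of these assumptions.

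**What to change.** Replace the conditional sentence in the SAP with the protocol's unconditional commitment: run the pattern-mixture analysis for 6-month FACT-G whatever the patterns and plots show, and report it beside the MAR result.

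Two additions go beyond what the protocol promised. The first should accompany the change: state in advance a range of shifts that may differ by arm, so that the model actually departs from MAR. The second is optional: identify deaths separately from other non-completers.

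The cost is a short SAP edit and a few extra model runs on data already collected. Nothing in the sample size, alpha, power or primary model changes.
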